The waiver will enable the study team to assess for necessary inclusion and exclusion criteria to prevent scheduling Veterans who would be ineligible for the study.

12.10g) The research could not practicably be conducted without access to and use of the PHI.

Agree Disagree

12.10g2) Describe why it would be impracticable to conduct this research without the PHI described 12.10a. (v3 /8/18)

Because inclusion and exclusion criteria can be found in PHI, it is important to access. This will save time and resources for both Veterans and research staff.

Section 13 - Alternatives to Participation

13) Describe the alternatives to participation in this research study (see ? for guidance)

Potential participants may seek care through the VA or in the community.

Section 14 - Potential Risks

14) Describe any potential or known risks or discomforts and assess their likelihood and seriousness (see ? for guidance)

At the initial assessment and other assessments for enrolled subjects, the interview questions and /or questionnaires may produce discomfort or anxiety from the discussion of personal, emotional, or anxiety-provoking topics. The methods used in the MAP and CBT-CP groups have been evaluated in prior studies with patients with chronic pain, and have been shown to be well-tolerated. Patient confidentiality will be protected to the extent permitted by law; however, there is always a risk of breach of confidentiality.

Section 15 - Risk Management

15) Describe the procedures for protecting against or minimizing any potential risks/discomforts, and the adequacy of resources for conducting the study and resources participants may need as a consequence of the research. When applicable, include detail of the following safety measures: (a) The type of safety information to be collected, including AEs; (b) Frequency of safety data collection; (c)

Frequency or periodicity of review of cumulative safety data; (d) Statistical tests for analyzing the safety data to determine if harm is occurring; and (e) Conditions that trigger an immediate suspension of the research. See ? for further requirements.

The following steps are taken to minimize risk.

- 1) To minimize the risk of patient discomfort, confidentiality will be stressed, participants will be offered breaks as needed, they will be informed that they have the right to refuse to answer questions or to terminate their participation in the study at any time without prejudice, and everyone who interacts with participants will be trained and supervised. Clinical staff will be available if immediate in-person evaluation is required for medical or mental health issues.
- 2) To minimize the risk of patients becoming more anxious or depressed, every patient will be given a 24-hour contact phone number to call in the event of increased depression or anxiety. If these symptoms are detected by either the research coordinator, research assistant, or the person conducting the intervention, [name], licensed psychologist and co-investigator, will be available to evaluate the patient and refer to appropriate treatment and notify the patient's other health care providers. When in doubt, the decision whether continued participation in the study is safe and clinically warranted will always be on the side of patient safety. Adverse events, including those unlikely to be the result of participation in the research (e.g., hospitalization due to an automobile accident), will be monitored at every study contact, including therapy as well as assessment sessions. They will be reported to the appropriate human subjects committees as per policy and to the Data Safety Monitoring Board for this study within the required time frame.
- 3) Veterans that report suicidal ideation at assessment or baseline/post-treatment assessment via the PHQ-9 or verbally will be further evaluated by the PI and [name]. Subsequent action will depend on the level of threat presented by the Veteran and may range from making a safety plan to implementing 5150 procedures for an inpatient hold. Further, suicidal ideation will be closely monitored during treatment by clinical observation and through comprehensive suicide risk assessments, which are part of standard VA care. Participants who develop suicidality during the treatment will be evaluated by the PI and [name] to determine whether continued participation in the study is safe and clinically warranted. If we and the participant believe that continued participation is contraindicated, an endpoint evaluation will be done and the participant will be referred for appropriate treatment. Appropriate treatment will depend on level of threat, and may include recommending a different form of psychotherapy that more directly addresses the predominant concern (e.g., depression, anxiety, PTSD, sleep, etc.), a referral to the participant's primary care provider or psychiatrist for medication management, referral to the Suicide Prevention Program at the VASDHS for passive suicidality, and/or hospitalization for imminent threat of suicide.
- 4) For participants who wish to terminate prematurely, we will request a final meeting to assess clinical status and safety and to review reasons for withdrawal (if the participant is willing to share them). Referrals for alternative mental health services, including those outside this protocol, will also be provided. Participants enrolled in the study may withdraw at any time without penalty or loss of any benefits or treatment options available to them. Investigators may also withdraw a participant from the study for treatment non-compliance or a newly developed psychiatric or medical problem if, in the opinion of myself and the study team, these factors interfere with the participant's ability to participate fully in the study. If a participant discontinues the study for any reason, he/she will be offered and allowed access to any care in our clinics that any other patient not associated with the study would receive.
- 5) Numerous steps will be taken to protect against social risks related to confidentiality. No personally identifiable information (PII) will exist on the intervention platform, the LifeData app, or with assessment data; data will be identified via subject ID number only. In addition, the intervention platform and LifeData dashboard utilize secure servers to protect participants' coded data and do not collect IP addresses (see Section 27.2d1). The master list linking ID numbers to participants' names will be stored locally on secure, restricted-access San Diego VA research servers in a password-protected database only accessible on password protected computers. Only IRB-approved research staff that has completed training in the handling of confidential data, and re-trained at least once annually, will have access to participant data and files. Last, no individual will ever be identified by name, audio recording, or other identifiers in professional presentations or manuscripts related to this study.

Section 17 - Potential Benefits

17) Discuss benefits that may be gained by the subject as well as potential benefits to society in general (see ?

for guidance)

Veterans may experience clinical improvement from participating in either intervention group (MAP or CBT-CP).

Section 18 - Risk/Benefit Analysis

18) Discuss why the risks to subjects are reasonable in relation to the anticipated benefits to subjects and in relation to the importance of the knowledge that may reasonably be expected to result.

Evidence from previous studies suggests that these interventions may reduce distress and improve quality of life. Some participants may also feel that they are making a useful contribution by furthering our understanding of how to treat chronic pain. We believe the benefits from this study outweigh its risks.

Section 20 - Compensation for Participation

20) Provide all details and justifications of the compensation plan. See ? for detailed requirements.

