Phase 2: Data from subject tracking logs will be used to determine the proportions of Veterans 1) who agree to be contacted out of the number approached about the study (general interest in the study), 2) who consent out of the number contacted (willingness to participate in the trial), 3) who attend the initial group meeting out of the number consented (enrollment), 4) who attend each class and complete the intervention out of the number who began (retention), and 5) reasons given for discontinuation. The number of contacts based on various recruitment strategies also will be recorded. Additional feasibility data includes: rate of missing data between treatment groups and per time point; differences in retention rate between treatment groups; factors influencing retention rate and their impact on study outcomes; completion of study measures and homework; and participants' satisfaction with study procedure and treatment delivery method. Further, age, gender, race/ethnicity, medications (including pain and other medications), and changes to medications/chronic pain treatments (TENS, injections, etc.), as well as pain etiologies (collected via chart review) will be explored within and between groups as they relate to study measures. This information will be helpful for assessing the feasibility of MAP and future hypothesis generation.

Additionally, we will examine the preliminary impact of MAP on pain interference (primary outcome), as well as pain acceptance, trait mindfulness, and pain catastrophizing (secondary outcomes). Other questionnaires that will be measured are listed in the *Questionnaires* section. Changes on these measures as well as participant satisfaction would also serve as indicators that MAP may be worthy of a future large-scale RCT.

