Initially, chi-squares and Analysis of Variance will be used to assess the effectiveness of the randomization procedures by comparing participants in each treatment condition on baseline variables. Within-group change will be assessed separately in MAP and CBT-CP groups on the primary (pain interference) and secondary clinical outcomes (pain acceptance, trait mindfulness, pain catastrophizing). We will plot means and standard deviations overtime to examine them visually, and determine the percentage of participants in each group that achieve minimally clinically important change on the BPI Pain Interference scale (1-point change, etc.). Additionally, we will use linear mixed-effects (LME) models to explore preliminary estimates of treatment effects. Time will be added as fixed effects in models, and the intercept will be added as a random effect. Effect size for within-group change will be calculated according to procedures described by Cohen, and interpreted with caution and in the context of the 95% confidence interval that surrounds it. The preliminary within-group treatment effects of MAP will help determine our future directions. For example, medium-large treatment effects would provide signal for future testing

whereas small treatment effects would suggest a need for additional development. Within the CBT-CP group, treatment effects will be examined in relation to findings from other published pain trials with similar Veteran populations to ensure adequacy of CBT-CP delivery.

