We will also conduct preliminary between-group comparisons on the BPI Pain Interference measure to better understand if continuing to pursue evaluation of MAP is warranted. Given that functional improvement is the ultimate goal of this research, we chose pain interference as the key outcome for the preliminary between-group analyses and power calculations because it is a proxy for functional improvement and one of the most commonly used outcome measure in psychosocial intervention trials of chronic pain. Group comparisons will be examined via LME with group (MAP vs. CBT-CP), time (10-total time points: baseline [1 time point], weekly during sessions [8 time points], post-intervention [1 time point]), and the treatment by time interaction added as fixed effects. The intercept will be added as a random effect. Effect size for the difference between groups will be calculated according to procedures described by Cohen. Effect size will be interpreted with caution, and in the context of the 95% confidence intervals that surrounds it.

Average time spent per week in meditation practice will be calculated from the LifeData mobile application or daily weekly diaries. The relationship between meditation practice time and study measures will be explored by adding the adherence rate to LME models as a covariate.

The actigraphy outcome will be the total activity count from each active interval, averaged across each 7-day observation period, excluding periods of missing data that occur due to temporary removal of the device. We will exclude participants that wear the Actiwatch < 5 valid days, with valid days defined as periods with < 4 hours of missing data. Participants will be instructed to press the event marker button on the Actiwatch to denote the times they get into and out of bed. Rest intervals (analogous to time in bed) will be scored manually using event markers, activity, and light, following the methodology of Patel et al. (2015), which takes into account that participants sometimes forget to press the event marker. Actigraphy data will be explored visually and via LME for trends of increased activity levels from baseline to post-intervention within group (Phase 1 and 2) and between groups (Phase 2) with guidance from [name] (statistical consultant), who has previous experience analyzing actigraphy data.

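### The Phase 2 plan specifies no between-arm estimate for the three named secondary outcomes; they are analysed only as separate within-arm changes.

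*Combined protocol and SAP*

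**What the plan says.** All the relevant text is in Section 9, Data and Data Analysis, Phase 2.

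- Pain interference is named as the primary outcome. Pain acceptance (CPAQ), trait mindfulness (MAAS) and pain catastrophizing (PCS) are the secondary outcomes. Changes on these measures are among the stated indicators that MAP may merit a large-scale RCT.
- The secondary outcomes are covered by this sentence: "Within-group change will be assessed separately in MAP and CBT-CP groups on the primary (pain interference) and secondary clinical outcomes". The accompanying mixed models are described as follows: "Time will be added as fixed effects in models, and the intercept will be added as a random effect". The effect size is Cohen's, for within-group change, read with its 95% CI. MAP's within-group effects are to guide future directions. CBT-CP's effects are to be set against published Veteran pain trials to check delivery.
- The arm contrast is then limited to one outcome: "We will also conduct preliminary between-group comparisons on the BPI Pain Interference measure". The reason given is that "we chose pain interference as the key outcome for the preliminary between-group analyses and power calculations". That model has group, time and their interaction over the ten BPI occasions: baseline, eight weekly sessions and post-intervention.
- Actigraphy is the only other outcome with a planned between-arm analysis.

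**The concern.** Phase 2 randomises therapy groups to MAP or CBT-CP, so a concurrent comparator exists for every scale completed in both arms. For the three secondary outcomes the plan does not use it.

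A within-arm change is uncontrolled. It contains any treatment effect, but also natural course, the non-specific effect of attending a group, and regression to the mean. Section 10 admits only Veterans scoring above 4/10 on pain severity and on at least one interference item. Scales that correlate with those items can therefore drift back without any treatment.

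This bears on the rationale. Sections 5 and 7 argue that formal meditation should strengthen psychological flexibility processes, and Section 7 lists acceptance and present-moment contact among them. Changes on these scales also feed the decision on a larger trial. Under the plan as written, that part of the signal rests on uncontrolled change within a randomised study.

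**Working it through.** **1. Sample size check.** Phase 1 has 20 and Phase 2 has 86; 20 + 86 = 106, the total in Section 2a. Twelve groups of 7 to 8 give 84 to 96, which contains 86. The plan mentions power calculations, but the text gives no alpha, power, effect size or SD, so no power figure can be reproduced. The point does not depend on one.

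**2. Is the contrast planned anywhere?**

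| Text in Section 9 | Outcomes covered | Between-arm term? |
|---|---|---|
| Within-group analysis | Primary and three secondary | No: time only, effect size within arm |
| Between-group comparison | BPI Pain Interference | Yes: group, time, group-by-time |
| Actigraphy | Activity count | Yes: "within group (Phase 1 and 2) and between groups (Phase 2") |
| Feasibility paragraph | Demographics, medications, pain etiologies | No arm contrast on the scales: these factors "will be explored within and between groups as they relate to study measures" |

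No passage supplies a MAP versus CBT-CP estimate for CPAQ, MAAS or PCS.

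**3. How precise would it be?** Completers are 86 × 0.80 = 68.8, or 34.4 per arm (equal split assumed). The baseline-to-follow-up correlation ρ is not given; 0.5 to 0.7 is assumed. In baseline-SD units, the 95% CI half-width is 1.96 × s × √(2/n). Here s = √(2(1−ρ)) for change scores and s = √(1−ρ²) for follow-up adjusted for baseline.

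| n per arm | ρ | Change score | Baseline-adjusted |
|---|---|---|---|
| 34.4 | 0.5 | ±0.47 | ±0.41 |
| 34.4 | 0.7 | ±0.37 | ±0.34 |
| 43 (no loss) | 0.5 | ±0.42 | ±0.37 |
| 43 (no loss) | 0.7 | ±0.33 | ±0.30 |

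Therapy groups are the unit of randomisation, six per arm, so m = 34.4/6 = 5.73 completers per group. The design effect is 1 + (m − 1) × ICC. With an assumed ICC of 0.05 to 0.10 it is 1.24 to 1.47, which multiplies the half-widths by 1.11 to 1.21. The documents give no ICC.

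**4. Why two within-arm results do not replace the contrast (illustration only).** Suppose both arms truly change by the same d, in SDs of change, with 34 per arm and no clustering. Let p be the noncentral-t power of a paired test at two-sided 0.05. The chance that exactly one arm's 95% CI excludes zero is 2p(1 − p).

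| d | p | 2p(1 − p) |
|---|---|---|
| 0.2 | 0.204 | 0.325 |
| 0.35 | 0.509 | 0.500 |
| 0.5 | 0.808 | 0.311 |
| 0.6 | 0.924 | 0.140 |
| 0.8 | 0.995 | 0.010 |

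So equal true change would look different between arms in about 31 to 50% of trials for d from 0.2 to 0.5, falling to about 1% at 0.8.

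**The case against.** The strongest reply is that this is a deliberate choice. The study is a pilot whose only stated hypothesis is feasibility, and Aim 3 asks for preliminary impact. The plan names pain interference as the key outcome for comparison and gives reasons. Keeping arm contrasts to one key outcome in a 12-group pilot is defensible. This stands, and it is why the point is an improvement and not an error. But a reason for making BPI the key outcome is not a reason to omit exploratory estimates elsewhere, and estimation with intervals needs no power calculation. Actigraphy, itself exploratory, already has a between-arm analysis.

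Four stronger readings are tempting, and the documents do not support them.

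- A reader might infer that the trial can give no between-arm information on these scales. Both arms complete the same scales, so a difference could be derived from the two changes. What is missing is a planned model, effect size and interval for it.
- A reader might infer that the arms will be compared by eye or by which one is significant. The plan describes neither. It plots means and SDs over time, sets no significance rule for within-arm change, and gives each arm's result its own use. The discordance figures show a risk for later readers of the results, not a planned step.
- A reader might infer a hypothesis that MAP beats CBT-CP on psychological flexibility processes. None is stated, and catastrophizing is not one of the six processes listed in Section 7.
- A reader might extend the 31 to 50% over three outcomes: 1 − (1 − 0.311)³ = 67% and 1 − (1 − 0.5)³ = 87%. That assumes independent outcomes, no clustering and changes in the range where discordance peaks. The scales are self-reports from the same people, and the plan's signal for further testing is a medium-to-large effect, where discordance drops quickly. The figure should carry no weight.

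It also stands that the added intervals will be wide. Section 9 assigns all MAP sessions to the PI and all CBT-CP sessions to one study therapist, so any arm difference is confounded with therapist.

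**Conclusion.** The point holds as a gap in the analysis plan. No between-arm estimate is specified for pain acceptance, trait mindfulness or pain catastrophizing, although changes on them count towards the case for a larger trial. It is not an internal contradiction, and the feasibility aims are unaffected.

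The conclusion follows from the wording alone and needs no assumed figure. The half-widths of about ±0.34 to ±0.47 baseline SD rest on 34.4 completers per arm, an equal split, ρ of 0.5 to 0.7 and no clustering. They show that the contrast would be imprecise. That imprecision exists whether or not it is reported, and it is better shown.

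**What to change.** For each of CPAQ, MAAS and PCS, add an exploratory between-arm model at that scale's own assessment times. Either group, time and group-by-time, or follow-up adjusted for baseline, would serve; name one in advance. The BPI model should not be copied unchanged: it treats baseline as one of ten outcome occasions and follows the weekly BPI schedule. Include a random effect for therapy group, because groups are randomised. This is an addition, since the BPI model as described has only a random intercept.

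Report the MAP minus CBT-CP difference with its 95% CI, labelled exploratory and without significance claims. Keep the within-arm changes as description, and state that arm and therapist cannot be separated.

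The cost is three model fits and a few sentences in the plan, with no extra participants or assessments, because Section 9.8 already lists these scales for all phases. The downside is three more exploratory contrasts with wide intervals.

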The study will involve ~106 Veterans in the San Diego area. We expect the demographic make-up to approximate that of the VASDHS. Inclusion criteria are: 1) diagnosis of a chronic, non-terminal pain condition, 2) pain most days (>3 days/week) for at least 6 months, and 3) average pain severity and interference with enjoyment of life and/or general activity >4/10 over the past

week, as measured by the PEG (described in 9.8 Questionnaires). The following are exclusion criteria: 1) serious or unstable medical or psychiatric illness (e.g., unmanaged psychosis, manic episode, or substance abuse within the past year) or psychosocial instability (e.g., homelessness) that could compromise study participation, 2) active suicidal ideation or history of suicide attempt within the past year, 3) current participation in group psychotherapy for pain or any type of individual psychotherapy, or 4) changes to professionally delivered pain or mood treatments (e.g., no discontinuation of a treatment; no increasing the dose of medication) one month preceding the baseline assessment.

Section 10.2 Pregnant Women

10.2a) Are pregnant women the focus of the research?

Yes No

10.2b) Provide the justification for including pregnant women and address any special risks, protections, and safeguards.

Pregnant women will not be excluded from the study as there is no known risk to the woman or fetus associated with the methods used in either intervention. No additional protections are needed.

10.2c) It is indicated that pregnant women are the focus of the research. All of the below must be certified to be true to permit enrollment of pregnant women.

1. Where scientifically appropriate, preclinical studies including studies on pregnant animals and clinical studies including studies on non-pregnant women, have been conducted and provide data for assessing potential risks to pregnant women and fetuses. *A description of such studies should be included in the project application.*
2. The risk to the fetus is caused solely by interventions or procedures that hold out the prospect of direct benefit for the woman or the fetus; or, if there is no such prospect of benefit, the risk to the fetus is not greater than minimal and the purpose of the research is the development of important medical knowledge which cannot be obtained by any other means.

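### The only effect-size criterion for taking MAP forward is its uncontrolled within-group change, and the plan does not say how this combines with the randomised comparison

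*Combined protocol and SAP*

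**What the plan says.** All of this is in Section 9, Data and Data Analysis (Phase 2), unless noted.

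- **Within-group analysis.** "Within-group change will be assessed separately in MAP and CBT-CP groups on the primary (pain interference) and secondary clinical outcomes". On size, "Effect size for within-group change will be calculated according to procedures described by Cohen", to be "interpreted with caution and in the context of the 95% confidence interval that surrounds it". The share of participants reaching a 1-point change on BPI Pain Interference is to be given for each group.
- **Use of the result.** "The preliminary within-group treatment effects of MAP will help determine our future directions". By way of example, "medium-large treatment effects would provide signal for future testing", whereas "small treatment effects would suggest a need for additional development". CBT-CP's own change is compared with published trials to check that CBT-CP was delivered adequately.
- **Between-group analysis.** A mixed model with group, time and their interaction compares MAP with CBT-CP on BPI Pain Interference, with an effect size and 95% interval. Its stated purpose is also to judge whether MAP merits further evaluation. No size of difference is named.
- **Other inputs to the decision.** Changes on the outcome measures and participant satisfaction (Section 9), and recruitment, retention above 80% and credibility/expectancy ratings (Section 6).
- **Selection.** Section 10 requires "average pain severity and interference with enjoyment of life and/or general activity >4/10" on the PEG. Section 9.8 describes the PEG as derived from the Brief Pain Inventory, whose interference scale is the primary outcome.

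**The concern.** The text calls MAP's pre-post change a treatment effect and attaches size labels to it. Three other things can enter that change:

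- regression to the mean, because entry depends on a score closely related to the outcome;
- natural course, attention and group contact;
- other treatment, because stability is required only for the month before baseline (Section 10), and later changes are recorded weekly (Section 9.8) but not removed from the estimate.

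Caution and a 95% interval deal with sampling error. They do not remove this bias, and the available text mentions neither regression to the mean nor non-specific change.

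The randomised arm shares much of this change, but its own change is used only to check delivery. The contrast between arms has no criterion, and nothing says which result prevails if MAP's own change is medium or large while the contrast is near zero. A follower of the text could then report a signal for MAP that CBT-CP shows equally.

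Separately, Cohen's procedures allow more than one denominator, and the labels small and medium depend on which is used.

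**Working it through.** **What can be reproduced.** The only figures behind either estimate are the Phase 2 sample size and attrition. 20 + 86 = 106 matches the stated total; 86/12 = 7.17 per group fits 7 to 8; 86 × 0.8 = 68.8, or about 34 completers per arm. The available text mentions power calculations but shows no SD, correlation, ICC, alpha, power or target effect, so every such value below is an assumption. Medium is read as d ≥ 0.5, the usual Cohen reading.

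**Step 1: regression to the mean with no treatment effect.** Assume a referred-population mean of 4.5 to 6.5, SD 2.2 and retest correlation r of 0.5 to 0.8. If selection acted on the outcome itself, the expected drop is SD(1 − r)λ(z), with z = (4 − mean)/SD and λ the normal density divided by the upper-tail probability. At mean 5.5 and r = 0.65: z = −0.68, λ = 0.42, drop = 2.2 × 0.35 × 0.42 = 0.32 points, or d = 0.20 on the SD of the selected sample. At the most extreme corner (mean 4.5, r = 0.5) the same formula gives 0.51.

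A simulation of 400,000 people applied the actual rule (pain intensity > 4 and at least one interference item > 4):

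| When the PEG is scored | Drop in BPI interference | Within-group d | Share dropping ≥ 1 point |
|---|---|---|---|
| Same occasion as baseline BPI | 0.12–0.75 | 0.06–0.47 | 26–45% |
| Earlier, states correlated 0.5 with baseline | 0.06–0.36 | 0.03–0.19 | 24–38% |
| Earlier, independent states | about 0 | about 0 | 23–33% |

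The documents describe a telephone check of initial eligibility before the baseline visit but do not fix the occasion of the PEG, so the row that applies is unknown. In the last row the mean change is zero, so much of the 1-point share is ordinary within-person variation.

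**Step 2: regression plus non-specific change.** The documents give no size for non-specific change, so let the two total d₀ with no specific effect. With n = 34 and r = 0.65, SE = √[2(1 − r)/n + d₀²/(2n)]. At d₀ = 0.4: √(0.0206 + 0.0024) = 0.151, and P(observed d ≥ 0.5) = 1 − Φ(0.1/0.151) = 26%. For d₀ = 0.3, 0.5 and 0.6 the probabilities are 9%, 50% and 73%.

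**Step 3: the denominator.** Dividing by the SD of change instead of the baseline SD multiplies d by 1/√(2(1 − r)), taking equal SDs at both times: 1.12, 1.29 and 1.58 at r = 0.6, 0.7 and 0.8. A baseline-SD d of 0.35 becomes 0.39, 0.45 or 0.55. Only the last crosses 0.5.

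**Step 4: precision of the contrast.** Half-width of the 95% interval for between-group d is 1.96√(2·DE/n), with DE = 1 + (m − 1)ICC and m = 34/6 = 5.67. Without clustering: 1.96 × √(2/34) = 0.48. At ICC 0.01, 0.05 and 0.10: 0.49, 0.53 and 0.58. This ignores any gain from baseline adjustment or repeated measures.

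**The case against.** The plan is more balanced than a quick reading suggests. A reader might infer that MAP's within-group effect is the go/no-go rule and that the randomised arm is left out. The documents do not support that: the wording is that the effect helps determine direction, the size labels are given as an example, and the between-group comparison serves the same decision. Nor is the 1-point percentage shown for MAP alone: it is planned for each group and no threshold is attached to it.

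A reader might also infer that regression to the mean alone would produce a medium effect. In the simulation of the entry rule it does not: it tops out at 0.47 and may be near zero if the PEG precedes baseline. The 0.51 from the simple formula needs selection on the outcome itself at the most extreme assumed values. The entry cut is only above 4/10, and at least six months of pain is required. Reaching medium generally needs non-specific change, whose size is not documented.

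Finally, the contrast has its own weaknesses. CBT-CP is an active treatment, so a null difference cannot separate both working from neither working. The MAP arm is delivered solely by the PI and the CBT-CP arm by another therapist, so therapist is confounded with arm. Power at d = 0.5 with 34 per arm is about 54% (two-sided 5%) before clustering.

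All of this stands. It rules out making the contrast the sole basis or a superiority test. It does not make an uncontrolled change a measure of MAP's effect, and it leaves open how the two results are to be combined.

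**Conclusion.** The point holds in this form: the only size criterion in the plan attaches to MAP's uncontrolled change, the randomised comparison for the same decision has none, the rule for combining them is unstated, and the standardiser is undefined. It should be changed, because the wording affects what the pilot can conclude.

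On size, regression to the mean contributes a d of about 0 to 0.47 under the assumed mean, SD, correlations and PEG timing, and may be small. Non-specific change is the firmer worry. If the two total 0.4 to 0.5, a medium result with no specific effect appears in about a quarter to a half of trials with 34 MAP completers. The denominator adds a factor of 1.12 to 1.58 at r = 0.6 to 0.8. None of these inputs comes from the documents.

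The point shows no error in the sample size, and it does not mean the trial lacks a control.

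**What to change.** Reword the decision paragraph in Section 9:

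1. State that MAP's within-group effect size is descriptive and is not by itself a signal for future testing.
2. Present within-group d and the 1-point percentages for both arms side by side, with d divided by the pooled baseline SD.
3. Read any efficacy signal from the planned MAP minus CBT-CP estimate on BPI Pain Interference, adjusted for baseline, with a 95% interval that allows for therapy-group clustering. Treat it as an estimate and not as a superiority test, and weigh it alongside the feasibility criteria.
4. State that a null contrast will not be read as MAP having no effect, given the active comparator and the confounding of therapist with arm.
5. State the occasion on which the PEG is scored, so that the scope for regression to the mean can be judged.

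The cost is a rewording and a modest change to the between-group model; no new data or participants are needed. The downside is that the contrast is imprecise, about ±0.48 SD with 34 completers per arm and wider with clustering, so the pilot's efficacy message will be more guarded.
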